7.1.2. Prior and Concomitant SLE Medications

All prior and concomitant use of SLE medications will be collected from at least 24 weeks prior to Screening through the end of study using the "Prior and Concomitant SLE Medications" eCRF form and summarized separately by treatment group for both the ITT and Safety Populations.

The number and percentage of patients with any prior or concomitant SLE medication will be summarized overall and by each Anatomical Therapeutic Chemical (ATC) level 3 term and PT. ATC level 3 terms will be presented in descending order of frequency overall, and alphabetically in the event of ties. PTs within each ATC level 3 terms will be presented in alphabetical order. At each level of summarization, patients will be counted once if they reported more than one medication or therapy within the same PT or ATC level 3 term.

All prior and concomitant SLE medications will be presented in a single listing for the ITT Population, with indication (LN, SLE besides LN, Other: Specify) clearly identified.

7.1.3. Other Prior and Concomitant Medications and Therapies

All other prior and concomitant medications and therapies (ie, those not listed above) will be collected from 60 days prior to Screening through end of study using the "Prior and Concomitant Medications" eCRF form and summarized separately by treatment group for the Safety and ITT Population.

The number and percentage of patients with any other prior medication, concomitant medication or therapy will be summarized overall and by each ATC level 3 term and PT. ATC level 3 terms will be presented in descending order of frequency overall, and alphabetically in the event of ties. PTs within each ATC level 3 terms will be presented in alphabetical order. At each level of summarization, patients will be counted once if they reported more than one medication or therapy within the same PT or ATC level 3 term.

For other concomitant medications in this section, rescue use is collected directly on the eCRF and will be summarized.

Prohibited medications will be identified through blinded manual review by Kezar. Details regarding the manual review process are found in the separate CEC Charter. Prohibited concomitant medications will be summarized separately in a similar manner as other concomitant medications.

All other prior and concomitant medications and therapies will be presented in a single listing for the ITT Population, with prohibited and rescue medications clearly identified.

7.1.4. Concomitant Procedures

All concomitant procedures will be collected on the "Concomitant Procedures" eCRF form and summarized separately by treatment group for the ITT Population.

The number and percentage of patients with any concomitant procedure will be summarized overall and by each ATC level 3 term and PT. ATC level 3 terms will be presented in descending order of frequency overall, and alphabetically in the event of ties. PTs within each ATC level 3 terms will be presented in alphabetical order. At each level of summarization, patients will be counted once if they reported more than one concomitant procedure with the same PT or ATC level 3 term.

All concomitant procedures will be listed for the ITT Population.

7.2. Study Treatments

See Section 3.3 for details regarding study treatment.

7.2.1. Extent of Exposure

Extent of exposure to study treatment will be summarized by treatment group using descriptive statistics for the Safety analysis set:

- Number of injections administered
- Number of Injections (%) administered: In Clinic, At Home (Self, Caregiver, or Medical Professional)

- Categorical number of doses received (1-10, 11-20, 21-30, 31-40, 41-50, >50)
- Total cumulative dose received (mg)
 - Calculated as sum of dose received (mg) across all administered injections
- Average dose received (mg)
 - Calculated as (total cumulative dose received/number of administered injections)
- Duration of exposure (weeks), ignoring any treatment interruptions
 - Calculated as [(date of last dose date of first dose + 1)/7]

All study treatment administration and exposure information, including at-home versus clinic administration, will be listed for the Safety Population. If applicable, a separate listing will be presented for study treatment exposure exceptions (study treatment not administered, full dose not administered, and/or study treatment not received as randomized).

7.2.2. Treatment Compliance and Modifications

The following treatment compliance and modification information will be summarized by treatment group using descriptive statistics for the Safety analysis set:

- Number and percentage of patients who:
 - Completed study treatment
 - Had at least one missed dose
 - Had at least one dose reduction (dose reduction only permitted in 60 mg treatment group per the protocol)
- Relative dose intensity (%)
 - Calculated as [(total cumulative dose received in mg/duration of exposure in days) / (total planned daily dose in mg/52)] * 100.
- Percent compliance with planned treatment regimen
 - Calculated as [(number of injections administered/52) * 100]
- Categorical percent compliance with planned treatment regimen ($\leq 50\%$, > 50-60%, > 60-70%, > 70-80%, > 80-90%, > 90-100%)

All compliance information will be listed for the Safety Population.

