3.3. Study Treatment

Zetomipzomib or placebo ("study treatment") will be administered by subcutaneous injection once weekly from Week 1 to Week 52 according to the Schedule of Assessments (Appendix 1). For all patients, the first and second doses of zetomipzomib or placebo will be administered at the clinical site. The first injection will be a 30-mg dose of zetomipzomib or placebo for all randomized patients. For patients randomized to 60 mg of zetomipzomib or placebo, the second and subsequent weekly injections will be at a 60-mg dose level of zetomipzomib or placebo. Patients randomized to 30 mg of zetomipzomib or placebo will continue to receive the 30 mg dose of zetomipzomib or placebo at all subsequent weekly injections.

After the second dose, zetomipzomib or placebo injections will either be administered by the patient/caregiver at home following training or via home health service at the patient's location, as appropriate, or by study personnel at the investigational site.

Subcutaneous injection sites should be rotated (eg, 4 abdominal quadrants, posterior upper arms, and anterior thighs), and a minimum of 4 weeks should separate injections to the same anatomic site, if possible.

See Section 7.1.1.1, Section 7.1.1.2, and Section 7.1.1.3 for information regarding protocol-required background medications (IV methylprednisolone, MMF, and oral corticosteroids, respectively).

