3.5. Randomization, Stratification, and Blinding

Patients who have provided informed consent (IC) and passed study inclusion/exclusion criteria per Sections 4.2 and 4.3 of the study protocol will be randomized via the system.

Patients will be randomized to receive either zetomipzomib (30 mg or 60 mg) or matching placebo in a 2:1:2:1 ratio (zetomipzomib 30 mg: 30 mg matching placebo: zetomipzomib 60 mg: 60 mg matching placebo). Randomization will occur at Day 1 (Week 1) prior to the first dose of zetomipzomib or placebo and will be stratified by:

- LN Class (Class III/IV +/- V and pure Class V)
- Average 24-hour UPCR at the Screening visit (\leq 3.0 and \geq 3.0)
- IV methylprednisolone planned total dose (0 to <500 mg, 500-1000 mg, or >1000 to 3000 mg) Note: no more than 20% of the patients may be stratified into the >1000 to 3000 mg group.

All study personnel and patients may know if the patient is in the low dose group (30 mg or matching placebo) or the high dose group (60 mg or matching placebo). Randomized treatment assignment within dose group (ie, to zetomipzomib or matching placebo) at the patient level will remain blinded to all patients and all Sponsor, contract research organization (CRO;), and site personnel involved in the day-to-day conduct of the study until the proper unblinding procedures have been followed. To preserve the blind with respect to active treatment and placebo, patients randomized to the placebo group will receive a subcutaneous injection in an equivalent volume to the active zetomipzomib injection and on the same dosing schedule.

Additional details regarding planned unblinding during the course of the study are documented in a separate Blinding Management Plan. Details regarding emergency unblinding of a patient due to safety concerns are documented in Section 3.2.3 of the study protocol and the User Manual. Any patients unblinded for safety reasons will be clearly identified in the data listings.

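### Relative dose intensity mixes exposure days, 52 weekly injections and an undefined daily dose, so a fully dosed patient scores 14.5%, about 750% or over 5,000% on its natural readings

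*SAP*

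**What the plan says.** SAP Section 7.2.2 defines relative dose intensity (%) as 100 times the following ratio: "total cumulative dose received in mg/duration of exposure in days) / (total planned daily dose in mg/52". The next measure in that list, percent compliance, reads "Calculated as [(number of injections administered/52) * 100", so there 52 is a count of planned injections.

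Section 7.2.1 specifies "Duration of exposure (weeks), ignoring any treatment interruptions" and computes it as the last dose date minus the first dose date plus one day, divided by 7. The relative dose intensity formula takes the same duration in days.

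Section 3.3 sets the schedule. Study treatment "will be administered by subcutaneous injection once weekly from Week 1 to Week 52". It adds: "The first injection will be a 30-mg dose of zetomipzomib or placebo for all randomized patients". The 60-mg level then receives 60 mg at every later injection, and the 30-mg level stays at 30 mg. Section 3.5 gives four randomized groups: "zetomipzomib 30 mg: 30 mg matching placebo: zetomipzomib 60 mg: 60 mg matching placebo".

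No section of either document defines a planned daily dose for study treatment. The SAP works with a total daily dose only for MMF and oral corticosteroids (Sections 7.1.1.2 and 7.1.1.3). Section 13, which lists changes to the planned analysis, does not touch the formula.

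**The concern.** The two halves of the ratio are on different time scales, and the planned quantity has no stated meaning. A relative dose intensity should read about 100% for a patient who receives everything on schedule. This one does so only if the programmer supplies a meaning that the SAP does not give.

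The measure has a job that the neighbouring lines do not do. Percent compliance counts injections, so it cannot see the reductions from 60 mg to 30 mg that SAP Section 3.4.1 allows. Average dose per injection cannot see missed doses. Relative dose intensity is the only listed percentage of plan that should reflect both. For example, a 60-mg patient who misses nothing but is reduced to 30 mg from injection 10 onward shows 100% compliance. That patient has received 30 + 8 × 60 + 43 × 30 = 1,800 mg of a planned 3,090 mg, or 58.3%.

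**Working it through.** The documents give no numeric value to reproduce, so the check applies the formula to a patient who receives all 52 injections on schedule.

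**Inputs**
- Planned and received dose (SAP 3.3): 30-mg level 52 × 30 = 1,560 mg; 60-mg level 30 + 51 × 60 = 3,090 mg.
- Duration (SAP 7.2.1): 51 × 7 + 1 = 358 days.
- Numerator: 1,560/358 = 4.358 mg/day; 3,090/358 = 8.631 mg/day.

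**The formula as written, by meaning of the planned daily dose**

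| Meaning | 30-mg level | 60-mg level |
|---|---|---|
| Total planned dose | 4.358/(1,560/52) = 14.5% | 8.631/(3,090/52) = 14.5% |
| Dose per injection | 4.358/(30/52) = 755% | 8.631/(60/52) = 748% |
| Daily equivalent of the weekly dose | 4.358/((30/7)/52) = 5,287% | 8.631/((60/7)/52) = 5,236% |

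The first row is 52/358 at both levels. Counting 364 days instead of 358 does not help: the rows become 14.3%, 743% and 736%, and 5,200% and 5,150%.

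**Readings that come near 100%**
- Adding one value of weekly dose/7 per week over 52 weeks, then dividing by 52: (1,560/7)/52 = 4.286 mg/day and (3,090/7)/52 = 8.489 mg/day. Both levels give 101.7%.
- Counting only the 52 dosing days as the duration, with the total planned dose below: 100%. This contradicts the first-to-last-dose duration in Section 7.2.1.

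**Units put right**

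Using 100 × (cumulative mg / weeks of exposure) / (total planned mg / 52), with 358/7 = 51.14 weeks, a completer scores 364/358 = 101.7% at both levels. Under the total-dose reading the slip is therefore a constant factor of 7 (101.7%/7 = 14.5%).

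**Separate effect of the duration convention**

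For n weekly injections with none missed, Section 7.2.1 gives 7(n − 1) + 1 days. This counts one day of the last dosing week and omits the other six. With units corrected:

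| Injections | Days | 30-mg level | 60-mg level |
|---|---|---|---|
| 1 | 1 | 700% | 353% |
| 4 | 22 | 127% | 112% |
| 10 | 64 | 109% | 105% |
| 26 | 176 | 103% | 102% |
| 52 | 358 | 101.7% | 101.7% |

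The 60-mg column is lower at early stops because the 30-mg first dose is set against a planned average of 3,090/52 = 59.42 mg per week.

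**The case against.** The strongest reply is that a reading exists that works. Weekly dose/7, totalled over 52 weeks and divided by 52, puts mg/day on both sides, keeps the first-to-last-dose duration and gives 101.7%. On this view the 748–755% and 5,236–5,287% figures are literal stress tests: the first ignores the word total, and the second divides a figure already in mg/day by 52 again. Only 14.5% is a likely slip, and it would be obvious at output review beside 100% compliance. The SAP also refers to table shells, which are not among the documents and might settle the meaning. Finally, the duration rule in Section 7.2.1 is explicit and consistent, so it is not an error.

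Some of this stands. The consequence is small, a visibly absurd value would probably be caught, the shells cannot be checked, and the duration rule is a legitimate convention.

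The rescue by the 101.7% reading does not stand. It adds 52 values of a daily quantity, one per week. Daily equivalents summed over all 364 days return the total planned dose (364 × 30/7 = 1,560 mg at the 30-mg level), and the score goes back to 14.5%. The SAP states no such sum. A formula that needs an unstated construction to give a sensible answer is wrong as written.

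**Conclusion.** The point holds and is minor. Followed as written, the formula scores a fully dosed patient 14.5%, 748–755% or 5,236–5,287%, depending on the meaning given to an undefined term. These figures assume 52 on-schedule weekly doses, the 30-mg first injection at both levels and the duration rule in Section 7.2.1.

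One descriptive line for the Safety Population is affected, together with any patient listing of it. Cumulative dose, average dose, number of injections, percent compliance and the counts of missed or reduced doses are specified separately and remain valid. Exposure-adjusted event rates have their own exposure definition (SAP 9.1.12). No efficacy result, power or type I error depends on this measure.

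**What to change.** Replace the formula in SAP Section 7.2.2 with:

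100 × (cumulative mg / weeks of exposure) / (total planned mg / 52)

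Define total planned mg from the Section 3.3 schedule as 1,560 at the 30-mg level and 3,090 at the 60-mg level, by the patient's assigned level, whether active or matching placebo. The level must be taken per patient because the pooled placebo group contains both. The cost is one line in the SAP and its program. Add a note that, with the Section 7.2.1 duration, a completer shows 101.7% and very early stoppers are inflated.

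If the sponsor wants exactly 100% for anyone with no missed or reduced dose, an optional definition is 100 × cumulative mg / mg planned over W weeks. Here W = (last dose date − first dose date + 7)/7, rounded to whole weeks, and planned mg is 30W at the 30-mg level or 30 + 60(W − 1) at the 60-mg level. This adds one derived variable, used for this line only.

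The optional version still responds to lost dose. At the 60-mg level, 8 of 52 injections missed with the first and last given yields 2,610/3,090 = 84.5% (85.9% under the unit fix alone). Reduction to 30 mg from injection 10 onward yields 58.3% (59.2% under the unit fix alone).

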8. EFFICACY ANALYSIS

Unless otherwise specified, all efficacy analyses will be performed for the ITT Population with Class III/IV+/- V LN only. In general, all efficacy data will be summarized by treatment group and visit and listed for the ITT Population.

Unless specified otherwise, all efficacy analyses involving treatment comparisons will be performed separately for the following pairwise comparisons:

- zetomipzomib 60 mg versus pooled placebo
- zetomipzomib 30 mg versus pooled placebo

No statistical comparisons will be performed between the zetomipzomib high and low dose groups.

Unless otherwise specified, all statistical tests will be 2-sided at the 5% level of significance. As applicable, 2-sided 95% CIs will be presented. For hypothesis testing nominal p-values will be presented (Protocol, Section 10.6).

8.1. Controlling for Type I Error

Formal statistical tests are planned for the primary and the following key secondary efficacy endpoints. The analyses will be performed based on patients in the ITT Population with Class III/IV+/- V LN only. Patients with pure Class V LN will not be included in the analyses involving hypothesis testing of the following endpoints.

Primary endpoint

• CRR at Week 37

Key secondary endpoints

- CRR at Week 53
- PRR at Week 37
- PRR at Week 53
- CRR at Week 25
- PRR at Week 25

The testing sequence will be performed independently for each zetomipzomib treatment group versus placebo (pooled).

Analysis of the primary endpoint will involve three pairwise comparisons:

- zetomipzomib 60 mg vs placebo
- zetomipzomib 30 mg vs placebo
- [(zetomipzomib 30 mg + zetomipzomib 60 mg) /2] vs placebo

The above treatment comparisons can be tested under the following hypotheses:

- Null hypothesis H₀: P0=P1=P2=0.20
- Alternative hypothesis (a): P1=P2=0.40, P0=0.20
- Alternative hypothesis (b): P1=0.20, P2=0.40, P0=0.20

where P0, P1 and P2 are the true CRR at Week 37 for placebo, and 2 zetomipzomib doses (30 mg and 60 mg), respectively.

Each of the three pairwise comparisons above are assessed at the 2-sided α =0.05 level. As such, the overall Type 1 error rate across the three comparisons will become higher but controlled at the 2-sided level of 0.096716.

For each of the three pairwise comparisons above, a family-wise type 1 error rate at the α =0.05 level (2-sided) level will be used for the analysis of the primary and 5 key secondary endpoints starting from the primary endpoint, so that statistical significance for any of the 5 key secondary endpoints can only be declared if the same comparison on the primary endpoint (primary estimand) achieves statistical significance at the 2 sided α =0.05 level. The Hochberg step-up method (Hochberg, 1988) will be applied to adjust for hypothesis testing of each pairwise comparison on all 5 key secondary endpoints and maintain the overall type I error rate at the α =0.05 level for each of the pairwise comparisons. Results from all statistical analyses, regardless of the level of significance, will be provided. Results that are statistically significant according to the Hochberg method will be indicated with a "*" next to the significant p-value.

For statistical tests that are planned but not performed as a result of the multiplicity adjustment procedure (ie, other secondary endpoints), as well as for any other comparisons that are not subjected to multiplicity adjustment, nominal 2-sided p-values (without adjustment for multiplicity) will be provided as a measure of the strength of association between the endpoint and the treatment effect rather than formal tests of hypotheses.

Other (non-key) secondary and exploratory endpoints will be analyzed without controlling for the global family-wise type I error rate.

8.2. Primary Efficacy Endpoint

The primary efficacy endpoint is the proportion of patients who achieve CRR at Week 37. See Section 3.2.1 for details. CRR at Week 37 will be adjudicated by the CEC, in accordance with procedures documented in the CEC Charter. Both the adjudicated and original (non-adjudicated, as programmed) primary endpoint information will be retained on the analysis database, but the adjudicated endpoint will be used for the primary analysis.

To be a responder, a patient must complete the Week 37 visit and not be considered a treatment failure as defined in Section 3.2.1.

8.2.1. Intercurrent Events and Estimands

Table 4: Intercurrent Events

Label	Description
IE1	 Treatment Failure as adjudicated by the CEC for any of the following criteria: Prednisone or equivalent beyond that permitted (see Protocol Section 6.2.1.2); MMF or equivalent >2 g/day after Week 25; Requiring rescue therapy (see Protocol Section 6.2.3 for details); Use of prohibited medications (see Protocol Section 6.2.4 and Protocol Section 13, Protocol Appendix 2 for details); Discontinuation of zetomipzomib or placebo
IE2	Discontinuation of Study
IE3	Death

CEC=Clinical Endpoint Committee; IE=intercurrent event; MMF=mycophenolate mofetil.

Table 5: Estimands for Comparative Analysis between Zetomipzomib and Placebo (Part 1 of 2)

Objective	Primary: To evaluate the efficacy of zetomipzomib compared to placebo in the treatment of active LN	Same as primary	Same as primary
Estimand Label	Primary Estimand	Secondary Estimand	Tertiary Estimand
Estimand Description (with Endpoint)	Treatment difference (Zetomipzomib – Placebo) in proportion of patients achieving CRR at Week 37	Same as primary	Same as primary
Target Population	Patients in the ITT Population with confirmed Class III/IV +/- V LN	Patients in the ITT Population with confirmed Class III/IV +/- V or pure Class V LN	Patients in the Per Protocol Population with confirmed Class III/IV +/- V LN
Endpoint	CRR at Week 37	Same as primary	Same as primary
Estimator	Cochran-Mantel-Haenszel (CMH) test at 2 sided 5% level of significance, stratified by the randomization stratification factors	Same as primary	Same as primary

Objective	Primary: To evaluate the efficacy of zetomipzomib compared to placebo in the treatment of active LN	Same as primary	Same as primary
Estimand Label	Primary Estimand	Secondary Estimand	Tertiary Estimand
Treatment Conditions	Zetomipzomib 30mg vs. Pooled 30mg and 60mg Placebo and Zetomipzomib 60mg vs. Pooled 30mg and 60mg Placebo and [(Zetomipzomib 60mg + Zetomipzomib 30mg)/2] vs. Pooled 30mg and 60mg Placebo	Same as primary	Same as primary
Population- Level Summary	Difference in proportion of patients achieving CRR at Week 37 between patients assigned to zetomipzomib versus patients assigned to placebo, regardless of adherence in patients with confirmed Class III/IV +/- V LN	Difference in proportion of patients achieving CRR at Week 37 between patients assigned to zetomipzomib versus patients assigned to placebo, regardless of adherence in patients with confirmed Class III/IV +/- V or pure Class V LN	Difference in proportion of patients achieving CRR at Week 37 between patients treated with zetomipzomib versus patients treated with placebo who were strictly compliant with the protocol without major protocol deviations with confirmed Class III/IV +/- V LN
IE1 (TF)	Composite Method	Composite Method	Composite Method
IE2 (Discontinue Study)	Composite Method	Composite Method	Composite Method
IE3 (Death)	Composite Method	Composite Method	Composite Method
Missing Data Handling	NRI will be used to impute missing primary endpoint data due to any of the following prior to Week 37: early study discontinuation, lost to follow-up.	Same as primary	Same as primary

Objective Estimand Label	Primary: To evaluate the efficacy of zetomipzomib compared to placebo in the treatment of active LN Primary Estimand	Same as primary Secondary Estimand	Same as primary Tertiary Estimand
Rationale for Strategies	Estimand to assess all randomized patients in confirmed Class III/IV +/- V, regardless of actual treatment received and assigning non-response to primary endpoint for all IEs by using the composite method. This estimand maintains the benefits of randomization, ensuring that treatment groups remain comparable, and the study reflects real-world conditions.	To assess patients in the same manner of the primary estimand but in patients with confirmed Class III/IV +/- V or pure Class V LN.	To assess the patients that were strictly compliant with the protocol without major protocol deviations. This estimand most closely assesses the treatment effect under ideal or optimal conditions where the treatment is administered exactly as planned. This approach is useful for Clinical Relevance, Internal Validity, and Interpretability.

CRR=complete renal response; IE=intercurrent event; IMP=investigational medicinal product; ITT=intent-to-treat population; LN=lupus nephritis; NRI=non-responder imputation; TF=treatment failure.

Table 5: Estimand for Comparative Analysis between Zetomipzomib and Placebo (Part 2 of 2)

Objective	Same as Primary	Same as primary	Same as primary	Same as primary
Estimand Label	Sensitivity 1 to Primary Estimand	Sensitivity 2 to Primary Estimand	Sensitivity 3 to Primary Estimand	Sensitivity 4 to Primary Estimand
Estimand/Sensitivity Analysis Description (with Endpoint)	Treatment difference (Zetomipzomib – Placebo) in proportion of patients achieving CRR at Week 37 as measured by logistic regression.	Treatment difference (Zetomipzomib – Placebo) in proportion of patients achieving CRR at Week 37 regardless of intercurrent events IE1-IE3.	Treatment difference (Zetomipzomib – Placebo) in proportion of patients achieving CRR at Week 37 in subset of population that did not require additional medication.	Treatment difference (Zetomipzomib – Placebo) in proportion of patients achieving CRR at Week 37 in subset of population who completed treatment through Week 37.
Target Population	Same as primary	Patients in the ITT Population with confirmed Class III/IV +/- V LN that had intercurrent events IE1- IE4.	Subset of patients in the ITT Population with confirmed Class III/IV +/- V LN who did not require additional medication (including rescue therapy and protocol prohibited medications) or change in background medications prior to Week 37	Subset of patients in the ITT Population with confirmed Class III/IV +/- V LN who completed treatment through Week 37
Endpoint	Same as primary	Same as primary	Same as primary	Same as primary
Estimator	Logistic regression model will include study treatment, region, baseline UPCR, and the stratification factors	Same as primary	Same as primary	Same as primary
Treatment Conditions	Same as primary	Same as primary	Same as primary	Same as primary

Objective	Same as Primary	Same as primary	Same as primary	Same as primary
Estimand Label	Sensitivity 1 to Primary Estimand	Sensitivity 2 to Primary Estimand	Sensitivity 3 to Primary Estimand	Sensitivity 4 to Primary Estimand
Population-Level Summary	Difference in proportion of patients achieving CRR at Week 37 between patients assigned to zetomipzomib versus patients assigned to placebo, regardless of adherence in patients with confirmed Class III/IV +/- V LN, while correcting for baseline factors	Difference in proportion of patients achieving CRR at Week 37 between patients assigned to zetomipzomib versus patients assigned to placebo, regardless of adherence and regardless of having intercurrent events IE1-IE4 in patients with confirmed Class III/IV +/- V LN	Difference in proportion of patients achieving CRR at Week 37 between patients assigned to zetomipzomib versus patients assigned to placebo, regardless of adherence in patients with confirmed Class III/IV +/- V LN who did not require additional medication (including rescue therapy and protocol prohibited medications) or change in background medications prior to Week 37	Difference in proportion of patients achieving CRR at Week 37 between patients assigned to zetomipzomib versus patients assigned to placebo, regardless of adherence in patients with confirmed Class III/IV +/- V LN completed treatment through Week 37
IE1 (TF)	Composite	Treatment Policy	Principal Stratum	Composite
IE2 (Discontinue Study)	Composite	Treatment Policy	Principal Stratum	Composite
IE3 (Death)	Composite	Composite	Composite	Composite
Missing Data Handling	Same as primary	All available assessments will be used, regardless of intercurrent events (except Death). Missing data will not be imputed, instead a Tipping Point Analysis will be performed.	Same as primary	Same as primary

Objective	Same as Primary	Same as primary	Same as primary	Same as primary
Estimand Label	Sensitivity 1 to Primary Estimand	Sensitivity 2 to Primary Estimand	Sensitivity 3 to Primary Estimand	Sensitivity 4 to Primary Estimand
Rationale for Strategies	Sensitivity analysis to the primary estimand which assess all randomized patients in confirmed Class III/IV +/- V, regardless of actual treatment received and assigning nonresponse to primary endpoint for all IEs by using the composite method. This sensitivity analysis uses logistic regression to allow for controlling baseline covariates.	This sensitivity to the primary estimand will include patients that had intercurrent events (except Death) to reflect that these intercurrent events could occur in practice and thus can be considered as an inherent part of the treatment.	This sensitivity analysis to the primary estimand includes patients who did not require additional medication (including rescue therapy and protocol prohibited medications) or change in background medications prior to Week 37 and thus summarizes the effect in this population.	This sensitivity analysis to the primary estimand includes patients who completed treatment through Week 37 and thus summarizes the effect in this population.

CRR=complete renal response; IE=intercurrent event; IMP=investigational medicinal product; ITT=intent-to-treat population; LN=lupus nephritis; NRI=non-responder imputation; TF=treatment failure.

